7.2 CONCOMITANT DISEASES AND MEDICATION

For this extension study, no information on historical medication is collected. For more details on that, please refer to the parent trial (1368-0032) results.

Analyses of concomitant diseases and medication will be based on the SAF.

Concomitant diseases will be coded according to the most recent version of MedDRA.

Concomitant medication will be coded according to the most recent version of the World Health Organisation – Drug Dictionary.

Concomitant diseases which are present at start of the study, as well as characteristics of the trial disease, will be descriptively summarised overall.

A medication will be considered concomitant to treatment, if it

- is ongoing at the start of trial treatment or
- starts within the on-treatment period (see [Section 6.1](#) for a definition of study analysis phases).

Concomitant medication use will be summarised with frequency and percentage of patients by ATC3 class and preferred name, overall.

Concomitant use of non-drug therapies will be summarized overall with frequency and percentage.

The relevance of the concomitant therapies to the evaluation of PK will be decided no later than at the RPM/DBLM.

7.3 TREATMENT COMPLIANCE

Treatment compliance will be summarised overall via total volume infused (as a % of planned) for the SAF using descriptive statistics (N, mean, SD, minimum, median, maximum). The volume injected (as a % of planned) is defined as the volume injected at a visit (in number of syringes as recorded in the eCRF), divided by 4 (the number of syringes the patient should have received).

For the patients who discontinued the study treatment prematurely, only the visits on or before premature discontinuation will be used for the calculation of overall compliance.

The number of patients who received a dose will be tabulated per visit.

7.4 PRIMARY ENDPOINT(S)

The primary endpoint for this trial is the number of patients with treatment emergent adverse events at Week 48.

7.4.1 Primary analysis of the primary endpoint(s)

The analysis of the primary endpoint will be descriptive in nature and will be a part of the Safety analyses described in detail in [Section 7.8](#).

The primary analysis will be performed on the SAF.

7.5 SECONDARY ENDPOINT(S)

7.5.1 Key secondary endpoint(s)

[figure not shown]
This section is not applicable as no key secondary endpoint has been specified.

7.5.2 (Other) Secondary endpoint(s)

All secondary efficacy endpoints will be analysed descriptively based on the FAS.

For continuous secondary efficacy endpoints (EASI Score and SCORAD Score), standard statistical parameters (as defined in [Section 7](#)) will be presented per group defined in [Section 6.1](#). Both absolute and percent change from baseline will be analysed as an outcome as well as the values recorded at the respective time points.

For binary endpoints (EASI50, EASI75, achieving at least 2-grade reduction from baseline to clear (0) or almost clear (1) in IGA), frequency tables will be provided per group defined in [Section 6.1](#).

7.7 EXTENT OF EXPOSURE

The number of subjects who received a dose of trial drug will be tabulated. The amount of treatment received will be summarised by descriptive statistics (N, mean, SD, minimum, median, maximum) per visit and overall. Additionally, number of injections administered (as defined in [Section 5.4.4](#)) overall will be displayed.

7.8 SAFETY ANALYSIS

All safety analyses will be performed based on the SAF following BI standards. No hypothesis testing is planned.

7.8.1 Adverse Events

AEs will be coded with the most recent version of MedDRA.

The analyses of AEs will be descriptive in nature. All analyses of AEs will be based on the number of patients with AEs and not on the number of AEs. System organ classes (if applicable) will be sorted according to the standard sort order specified by the EMA, preferred terms (if applicable) will be sorted by total frequency (within system organ class) across all treatment arms.

For further details on summarization of AE data, please refer to “Analysis and Presentation of Adverse Event Data from Clinical Trials” [BI-KMED-BDS-HTG-0066] (4) and “Handling of missing and incomplete AE dates” [BI-KMED-BDS-HTG-0035] (3).

The analysis of AEs will be based on the concept of treatment emergent AEs. If only the start date of an AE is collected (without start time), any AE occurrence on the same day as the first BI 655130 administration will be assigned to the on-treatment phase.

An overall summary of AEs will be presented by treatment.

This overall summary will include summary statistics for the class of other significant AEs (sponsor definition based on ICH E3 (6)) and for the class of AESIs.

The following are considered an AESI in this trial:

- Hepatic injury
- Systemic hypersensitivity reactions including anaphylactic reaction
- Severe infections (according to RCTC grading in the ISF)
- Opportunistic and mycobacterium tuberculosis infections

The investigator has to classify on the eCRF whether an observed AE was an AESI or not. Only those AEs that are indicated by the investigator as AESI in the eCRF will be analysed in this category.

Based on the specification provided in ICH E3 (6), the sponsor has defined AEs which are to be classified as ‘other significant’. These will include those non-serious AEs which were reported with ‘action taken = Drug withdrawn’ or ‘action taken = Dose reduced’.

The frequency of patients with AEs will be summarised by treatment, primary system organ class and preferred term. AEs which were considered by the investigator to be drug related will be summarised separately (secondary safety endpoint of this trial). Separate tables will also be provided for patients with SAEs, patients with drug-related SAEs, patients with AESIs, patients with AE leading to discontinuation of the trial, and patients with other significant AEs (as described previously). AEs will also be summarized by maximum RCTC grade.

A summary of user-defined AE concepts (UDAEC) will be presented by treatment group. The UDAEC are presented in the table below.

Table 7.8.1: 1 Project MedDRA search criteria for User Defined Adverse Event Concepts

User Defined AE Concepts	Categories
Hypersensitivity ALL	Combined search strategy based on the three individual UDAECs described below (Anaphylactic reaction, Angioedema, Hypersensitivity)
Anaphylactic reaction	Narrow SMQ “Anaphylactic reaction”
Angioedema	Narrow SMQ “Angioedema”
Hypersensitivity	Narrow SMQ “Hypersensitivity”
Infections ALL	Combined search strategy based on the individual UDAECs described below (Severe infections, Opportunistic infections, Tuberculosis infections, and Serious infections); Severe infections investigator-defined will be disregarded for this search.
Severe infections (according to RCTC grading)	SOC Infections and infestations of at least severe RCTC grade, by HLGT
Serious infections	SOC Infections and infestations reported as serious AEs
Opportunistic infections	SMQ Opportunistic Infections (narrow)
Tuberculosis infections	BIcMQ sub-search 8.2 “Tuberculosis related terms”, narrow
Malignant tumours	Narrow Sub-SMQ “Malignant tumours” Narrow Sub-SMQ “Haematological malignant tumours” Narrow Sub-SMQ “Non-Haematological malignant tumours”
Malignant skin tumours	Broad Sub-SMQ “Skin malignant tumours”
Skin melanomas	HLT Skin melanomas (excl. Ocular)
Non-melanoma skin cancer (NMSC)	Broad sub-SMQ “Skin Malignant tumors” excluding HLT skin melanomas (excl. ocular)
Malignancies excluding NMSC	Sub-SMQ “Malignant tumours” excluding NMSC, whereas NMSC is defined above
Torsades de pointes	Broad sub-SMQ “Torsades de pointes/QT prolongation”

Table 7.8.1:1 Project MedRDA search criteria for User Defined Adverse Event Concepts (cont.)

DRESS (Drug reaction with eosinophilia and systemic symptoms syndrome), narrow	SMQ "Drug reaction with eosinophilia and systemic symptoms syndrome", narrow
DRESS (Drug reaction with eosinophilia and systemic symptoms syndrome), broad	Algorithmic SMQ on "Drug reaction with eosinophilia and systemic symptoms syndrome", broad Algorithm: A or (B and C and D) or (B and C and E) or (B and D and E)
Depression	sub-SMQ "Depression (excl suicide and self-injury)", broad
Suicidal ideation and behavior (SIB)	sub-SMQ "Suicide/self-injury"

For disclosure of AE data on ClinicalTrials.gov, the frequency of patients with non-serious AEs occurring with an incidence of greater than 5% (in preferred terms) will be summarised by treatment, primary system organ class and preferred term. The frequency of patients with SAEs will also be summarised.

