1.3 RATIONALE FOR PERFORMING THE TRIAL

The purpose of the trial is to offer to all patients who completed the clinical trial 1368-0032 as planned, the option to continue to receive BI 655130 treatment if they have responded to treatment and meet all criteria for study entry.

This trial is designed to evaluate the long-term tolerability and safety of BI 655130 in patients with AD. The data generated from this extension trial is anticipated to provide additional safety data of up to approximately four years treatment in approximately 40 patients treated with BI 655130.

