3.3.4.2 Withdrawal of consent to trial participation

Patients may withdraw their consent to trial participation at any time without the need to justify the decision.

If a patient wants to withdraw consent, the investigator should be involved in the discussion with the patient and explain the difference between trial treatment discontinuation and withdrawal of consent to trial participation, as well as explain the options for continued follow-up after trial treatment discontinuation, please see [Section 3.3.4.1](#) above.

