6.2.3 End of Treatment and Trial Completion

For all treated patients termination of trial medication and trial completion must be recorded on the corresponding eCRF.

For the comprehensive list of the trial procedures required at the EOT and the EOS visits please refer to [Flow Chart](#).

The EOS visit must be performed 16 weeks after the date of last drug administration.

Early Treatment and Trial Discontinuation:

If trial treatment is discontinued prematurely prior to the planned [Flow Chart](#) EOT visit, every effort should be made to have the patient return and undergo the procedures for the EOT visit as well as the EOS visit 16 weeks after the last study drug administration as outlined in the [Flow Chart](#).

Patients who are unable to physically return to the study site for the EOT and EOS visits should be contacted by the site by phone to collect information pertaining to adverse events and changes to concomitant therapy.

Trial Completion:

Trial completion is defined as a patient having reached the EOS visit within the specified window per protocol.

Treatment Completion:

Treatment completion is defined as a patient completing Visit 52 which is the EOT visit after receiving approximately 4 years of treatment

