7.2.5 Safety analyses

Adverse events will be coded using the Medical Dictionary for Drug Regulatory Activities (MedDRA). Standard BI summary tables and listings will be produced. All adverse events with an onset between start of treatment and end of the REP, a period of 16 weeks after the last dose of trial medication, will be assigned to the on-treatment period for evaluation.

All treated patients will be included in the safety analysis. In general, safety analyses will be descriptive in nature and will be based on BI standards. No hypothesis testing is planned.

Statistical analysis and reporting of adverse events will concentrate on treatment-emergent adverse events, i.e. all adverse events occurring between start of treatment and end of the REP. Adverse events that start before first drug intake and deteriorate under treatment will also be considered as 'treatment-emergent'.

Frequency, severity, and causal relationship of adverse events will be tabulated by system organ class and preferred term after coding according to the Medical Dictionary for Drug Regulatory Activities (MedDRA).

Laboratory data will be analysed both quantitatively as well as qualitatively. The latter will be done via comparison of laboratory data to their reference ranges. Values outside the reference range as well as values defined as clinically relevant will be summarised. Groups (defined in [Section 7.2.1](#)) will be compared descriptively with regard to distribution parameters as well as with regard to frequency and percentage of patients with abnormal values or clinically relevant abnormal values.

Vital signs, physical examinations, or other safety-relevant data observed at baseline, during the course of the trial and at the end-of-trial evaluation will be assessed with regard to possible changes compared to findings before start of treatment.

[REDACTED]

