5. ENDPOINT(S)

For all endpoints and unless explicitly specified otherwise, Week numbers refer to specific Visit numbers using extended time windows as defined in [Table 6.7: 1](#).

For all endpoints and unless explicitly specified otherwise, End-of-Study visit refers to V53 (Week 220), using extended time windows as defined in [Table 6.7: 1](#).

For handling of missing data and corresponding sensitivity analyses, see [Section 6.6](#).

Definition of baseline is provided in [Section 6.7](#).

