7. PLANNED ANALYSIS

All efficacy and safety analyses will be purely exploratory in nature. The following analyses are planned throughout the trial.

- **Status review (at the requested timelines)**

The status reviews will be performed periodically and on demand. The analyses will include all data available at the time of the snapshot. The analyses are planned to be defined for each time point as requests in the CSAP, depending on the requirements.

- **Final analysis (Week 220)**

The analysis of the entire efficacy, safety, PK, and biomarker data collected through the full 220 weeks of follow-up will be performed once all entered patients have completed the trial (up to EoS Visit); at that time point, a final database lock will be done and all data through week 220 will be reported. The majority of biomarkers will be reported outside the CTR.

General Remarks

The format of the listings and tables will follow the BI guideline “Standards for Reporting of Clinical Trials and Project Summaries” [BI-KMED-BDS-HTG-0045] (7) with the exception of those generated for PK.

The individual values of all patients will be listed, including those collected during the off-treatment period. Listings will generally be sorted by country, centre number, patient number and visit (if visit is applicable in the respective listing). AE listings will be sorted by treatment (see [Section 7.8.1](#) below for details).

The following standard descriptive statistical parameters will be displayed in summary tables of continuous variables:

N	number of non-missing observations
Mean	arithmetic mean
SD	standard deviation
Min	minimum
Q1	lower quartile
Median	median
Q3	upper quartile
Max	maximum

The data format for descriptive statistics of concentrations will be identical with the data format of the respective concentrations.

Statistical parameters will be displayed to a defined number of decimal places as specified in the BI guideline “Standards for Reporting of Clinical Trials and Project Summaries” (7).

Tabulations of frequencies for categorical data will include all possible categories and will display the number of observations in a category as well as the percentage (%) relative to the respective treatment. Percentages will be rounded to one decimal place. The category missing will be displayed if and only if there actually are missing values. Percentages will be based on all patients in the respective patient set whether they have non-missing values or not.

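### Adverse events are planned only as crude patient percentages although follow-up can run from about 16 to 220 weeks; add first-event rates per 100 patient-years beside them

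*SAP*

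**What the plan says.** **Counting unit and denominator.** SAP 7.8.1: "All analyses of AEs will be based on the number of patients with AEs and not on the number of AEs". This covers the tables by system organ class and preferred term, drug-related AEs, SAEs, AESIs, AEs leading to discontinuation, other significant AEs, maximum RCTC grade and the user-defined AE concepts. SAP 7 adds: "Percentages will be based on all patients in the respective patient set whether they have non-missing values or not".

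**Horizon.** At the final analysis "all data through week 220 will be reported". Protocol 1.3 gives the purpose as "additional safety data of up to approximately four years treatment".

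**AE window.** Protocol 7.2.5 evaluates as on-treatment "All adverse events with an onset between start of treatment and end of the REP", the residual effect period (REP) being 16 weeks after the last dose. SAP Table 6.1:1 instead closes the on-treatment phase at the EoT visit date plus one day.

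**How follow-up can be shortened.** Protocol 3.3.4.1 ends treatment for several reasons, among them patient choice, more than three consecutive missed doses, adverse events and rescue medication for worsening disease. Protocol 6.2.3 then says: "The EOS visit must be performed 16 weeks after the date of last drug administration". Protocol 3.3.4.2 adds: "Patients may withdraw their consent to trial participation at any time without the need to justify the decision".

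**Groups.** SAP 6.1 defines displays by parent-trial treatment sequence and by Week 16 response. Protocol 7.2.2 applies these groups to the primary endpoint, patients with treatment-emergent AEs at Week 48.

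**Exposure.** SAP 7.7 summarises the amount of treatment and the number of injections. It does not mention time at risk or link exposure to AE frequencies.

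**The concern.** A patient percentage is easy to interpret when everyone is observed for about the same time. Here the schedule allows very different observation times, and the time can depend on how the patient is doing. Protocol 1.4.2 itself expects lower exposure than in the parent trial and a risk of lost response, and rescue use ends treatment.

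Two things follow for tables that cover the whole trial. A common category such as any treatment-emergent AE drifts towards 100% and stops distinguishing a low rate from a high one. For SAEs, AESIs or malignancies the percentage does not saturate, but it rises with time observed, so a group that stays longer can look less safe for that reason alone. Crude percentages also do not show the information that up to four years of observation adds, which is the reason for running the extension.

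**Working it through.** **1. Follow-up range (from the documents).** Last scheduled dose at Week 204, EOS 16 weeks later: 204 + 16 = 220 weeks. Day = 7 × 220 + 1 = 1541, which matches the flow chart. 220 × 7 / 365.25 = 4.22 years. Shortest complete follow-up is one dose plus 16 weeks. Ratio 220 / 16 = 13.75, or more if consent is withdrawn early.

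**2. Saturation.** The documents give no AE rate for this population, so the 48-week risk r is assumed, with a constant hazard. Risk by Week 220 = 1 − (1 − r)^(220/48).
- r = 0.5: 1 − 0.5^4.583 = 95.8%
- r = 0.7: 1 − 0.3^4.583 = 99.6%

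**3. Dependence on observation time.** Crude percentage = 100 × [1 − exp(−rate × weeks × 7 / 365.25)], with assumed rates per patient-year (PY). The 64-week column is a patient whose last dose is at Week 48.

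| Rate per PY | 16 wk | 48 wk | 64 wk | 220 wk |
|---|---|---|---|---|
| 0.05 | 1.5 | 4.5 | 5.9 | 19.0 |
| 0.1 | 3.0 | 8.8 | 11.5 | 34.4 |
| 0.25 | 7.4 | 20.5 | 26.4 | 65.1 |
| 0.5 | 14.2 | 36.9 | 45.8 | 87.9 |
| 1 | 26.4 | 60.1 | 70.7 | 98.5 |
| 2 | 45.8 | 84.1 | 91.4 | 100.0 |

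- Same rate, different time: 0.1 per PY gives 11.5% against 34.4% (64 against 220 weeks).
- Different rate, same time: 1 against 2 per PY shows as 98.5% against 100.0% at 220 weeks, but 60.1% against 84.1% at 48 weeks.
- Reversal: 0.5 per PY over 64 weeks gives 45.8%, below the 65.1% from half that rate (0.25) over 220 weeks.

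**4. What a rate does.** Take 20 patients at 64 weeks and 20 at 220 weeks, both at 0.1 per PY. Expected patients with an event over first-event person-time: 2.3 / 23.1 PY and 6.9 / 68.8 PY, both 10 per 100 PY.

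**5. Zero events in 40 patients.** The exact two-sided 95% upper limit on the proportion is 1 − 0.025^(1/40) = 8.8%, whatever the follow-up. On person-time the limit is −ln(0.025) / PY = 3.69 / PY:
- all reach Week 220: 40 × 220 × 7 / 365.25 = 169 PY, limit 2.2 per 100 PY
- half stop at 64 weeks: 109 PY, limit 3.4 per 100 PY
- all stop at 16 weeks: 12 PY, limit 30 per 100 PY

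**The case against.** The case against is substantial, and several stronger readings fall to it.

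- **That the plan excludes time-scaled AE output.** A reader might infer this, but the sentence in 7.8.1 fixes the counting unit, not the denominator of every table. A first-event rate is itself a count of patients. Section 7.8.1 also refers to a sponsor standard on AE presentation that is not among the documents, and parts of SAP 5.4 are not visible. Only the absence from the visible text can be claimed.
- **That the primary endpoint saturates.** It is nominally fixed at Week 48, so the Week 220 figures do not describe it. Unequal follow-up still matters inside 48 weeks: at an assumed 0.5 per PY, 20 against 48 weeks gives 17.4% against 36.9%. Neither document says how AEs are cut at Week 48, and SAP 6.7 says AE analysis is not visit-based; that is a separate gap.
- **That group differences are produced by exposure.** The documents give no exposure by group. The rescue rule makes unequal exposure plausible, no more. For SAEs and AESIs, a split by parent-trial group rests on the general sentence in SAP 6.1, since 7.8.1 itself tabulates by treatment.
- **That the safety report would carry no information.** The breakdowns by term, seriousness, relatedness and grade, with the individual listings, remain useful.
- **That the gain is small.** By group this largely stands. Assuming 10 patients followed 4.2 years (42 PY), 5 per 100 PY gives about 2 events and an exact 95% CI of roughly 0.6 to 17 per 100 PY. Overall, step 5 shows a real gain.

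**Conclusion.** The point holds as a reporting weakness that should be corrected. The visible SAP specifies AE frequencies only as crude patient counts and percentages, while observation time can differ almost 14-fold or more between patients and can depend on response. In whole-trial tables the any-event category can reach about 96% to 99.6%, and percentages for rarer events can differ about threefold between 64 and 220 weeks at the same underlying rate (5.9% against 19.0% at 0.05 per PY; 11.5% against 34.4% at 0.1 per PY). Group differences can partly reflect exposure; the documents do not show that they will.

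These sizes rest on assumed event rates, a constant hazard, and whole groups sharing one follow-up time, which the documents do not state. The trial is single-arm and descriptive, so the effect is on interpretation and not on any error rate. If the sponsor's AE standard already produces exposure-adjusted rates, stating so in 7.8.1 would largely close the point.

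**What to change.** In SAP 7.8.1, beside the crude percentages, report for any treatment-emergent AE, SAEs, AESIs and the user-defined AE concepts:

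- the number of patients with a first event, total patient-years at risk, and the rate per 100 patient-years with an exact Poisson 95% CI;
- primarily overall, and descriptively by the Section 6.1 groups.

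Count time at risk from first dose to the earliest of first event, the end of the protocol's treatment-emergent window (16 weeks after the last dose), or end of participation.

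Before that, reconcile SAP Table 6.1:1 with Protocol 7.2.5. Censoring at the end of the SAP's on-treatment phase could drop events in the residual effect period, and the rates would not match the percentages beside them. Numerator, denominator and crude percentage must use the same window.

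Cost: a little more programming, using dosing and AE onset dates that the trial already records; a footnote that the rate assumes a roughly constant hazard; and wide intervals in the small groups, which should be shown as they are.

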5.2.6.1.4 Adverse events of special interest

The term adverse events of special interest (AESI) relates to any specific AE that has been identified at the project level as being of particular concern for prospective safety monitoring and safety assessment within this trial, e.g. the potential for AEs based on knowledge from other compounds in the same class. AESIs need to be reported to the sponsor’s Pharmacovigilance Department within the same timeframe that applies to SAEs, please see [Section 5.2.6.2.2](#). Refer also to [Section 1.4.2](#) and [Section 4.2.1](#)

The following are considered as AESIs:

Hepatic injury

A hepatic injury is defined by the following alterations of hepatic laboratory parameters:

- An elevation of AST (Aspartate Aminotransferase) and/or ALT (Alanine Aminotransferase) ≥ 3 fold ULN combined with an elevation of total bilirubin ≥ 2 fold ULN measured in the same blood draw sample, or
- Aminotransferase (ALT, and/or AST) elevations ≥ 10 fold ULN.

These lab findings constitute a hepatic injury alert and the patients showing these lab abnormalities need to be followed up according to the “DILI checklist” provided in the ISF.

In case of clinical symptoms of hepatic injury (icterus, unexplained encephalopathy, unexplained coagulopathy, right upper quadrant abdominal pain, etc.) without lab results (ALT, AST, total bilirubin) available, the investigator should make sure these parameters are analysed, if necessary in an unscheduled blood test. Should the results meet the criteria of hepatic injury alert, the procedures described in the DILI checklist should be followed.

Systemic hypersensitivity reactions including anaphylactic reaction

Any suspicion of severe systemic hypersensitivity reaction and of any potential cases of anaphylaxis should be defined and assessed using the criteria discussed in the statement paper from Sampson HA ([Appendix 10.1, R11-4890](#)).

Severe infections (according to RCTC grading in the ISF)

Opportunistic and mycobacterium tuberculosis infections

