The frequency of patients with AST or ALT elevations $\geq 3xULN$, $\geq 5xULN$, $\geq 10xULN$, and $\geq 20xULN$ will be displayed based on standardized laboratory values. To support analyses of liver related adverse drug effects, the frequency of patients with AST and/or ALT $\geq 3xULN$ combined with a total bilirubin $\geq 2xULN$ in a 30 day period after AST/ALT elevation will be displayed, stratified by alkaline phosphatase $< 2xULN$ and $\geq 2xULN$ (a patient can potentially be in both alkaline phosphatase strata in case of multiple AST/ALT and bilirubin elevations). The start of the 30 day time span is triggered by each liver enzyme elevation above the defined thresholds. This analysis will be based on standardized laboratory values. A graphical analysis of the ALT and total bilirubin during the on-treatment period will also be performed; the so called eDISH plot. In the graph, for each subject, the peak total bilirubin is presented as a fold increase over the ULN against the peak ALT as a fold increase over the ULN, on a log₁₀ scale. The measurements displayed of total bilirubin and ALT may, or may not, occur on the same date. Two reference lines, 2xULN for total bilirubin and 3xULN for ALT, are drawn onto the graph in order to divide the plane into four quadrants. Normal cases are in the lower left quadrant, potential DILI cases are in the upper right quadrant (Hy's Law quadrant), while the lower right quadrant is known as the Temple's corollary range (ALT $\geq 3xULN$ and total bilirubin $< 2xULN$).

Clinically relevant findings in laboratory data will be reported as baseline conditions (at screening) or as AEs (during the trial) if judged clinically relevant by the investigator, and will be analysed as such.

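### The AESI table counts only investigator-ticked events; hepatic injury needs a count derived by the protocol's own laboratory rule, and ticks should be reconciled with the definitions

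*SAP*

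**What the plan says.** **Protocol 5.2.6.1.4** names four AESI classes.

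- Hepatic injury is a laboratory definition: "A hepatic injury is defined by the following alterations of hepatic laboratory parameters". Limb 1 is AST and/or ALT of at least 3 times ULN, "combined with an elevation of total bilirubin ≥ 2 fold ULN measured in the same blood draw sample". Limb 2 is "Aminotransferase (ALT, and/or AST) elevations ≥ 10 fold ULN".
- Severe infection is set by RCTC grade.
- Opportunistic and mycobacterial infection is set by a list of named conditions.
- Systemic hypersensitivity starts from the investigator's suspicion, assessed against published clinical criteria.

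**SAP 7.8.1** repeats the four headings, has the investigator classify each AE on the eCRF, and then states: "Only those AEs that are indicated by the investigator as AESI in the eCRF will be analysed in this category". The category feeds a line of the overall AE summary and a separate table ("patients with AESIs, patients with AE leading to discontinuation of the trial" are among the tables listed).

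**SAP Table 7.8.1:1** adds user-defined AE concepts that do not depend on the tick. They cover severe, serious, opportunistic and tuberculosis infections, and anaphylaxis, angioedema and hypersensitivity. None covers hepatic injury.

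**SAP 7.8.2** tabulates patients with AST or ALT at or above 3, 5, 10 and 20 times ULN. It also tabulates patients with AST and/or ALT of at least 3 times ULN and total bilirubin of at least 2 times ULN "in a 30 day period after AST/ALT elevation will be displayed, stratified by alkaline phosphatase". An eDISH plot is added.

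**The concern.** Three of the four AESI classes have criteria that can be checked without the investigator's opinion, yet the AESI count rests on that opinion alone. For hepatic injury two investigator decisions are involved. Under SAP 7.8.2 a laboratory finding becomes an AE only if the investigator judges it clinically relevant, and under SAP 7.8.1 that AE must then be ticked. The protocol definition contains neither condition.

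At stake is the completeness and internal consistency of the safety report in a trial whose main purpose is long-term safety. Drug-induced liver injury is the first entry in the protocol's risk table, which points to the AESI section as mitigation. A reader could find zero hepatic AESIs in one table and a qualifying patient in a laboratory table, with nothing in the SAP to explain the difference.

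**Working it through.** The plan gives no figure on this point: protocol 7.5 states that no sample size calculation was done. The check is therefore a comparison of rules, followed by the size of one missed case.

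**Step 1. Set the classes side by side.**

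| AESI class | Protocol definition | Tick-independent output in the SAP |
|---|---|---|
| Hepatic injury | Two laboratory limbs | No concept; laboratory tables only |
| Severe infection | RCTC grade | Infection SOC at severe grade or worse |
| Opportunistic / TB infection | Named list | Narrow SMQ; BIcMQ sub-search |
| Systemic hypersensitivity | Suspicion plus clinical criteria | Three narrow SMQs, combined |

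The infection and hypersensitivity searches approximate the protocol definitions; they do not copy them.

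**Step 2. Write the hepatic rules formally.** For each blood draw let *a* be the larger of AST and ALT, and *b* total bilirubin, both as multiples of ULN.

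- Protocol: some draw has (*a* ≥ 3 and *b* ≥ 2), or *a* ≥ 10.
- SAP 10-fold table: some draw has *a* ≥ 10.
- SAP 30-day table: some draw has *a* ≥ 3, and a draw 0 to 30 days later has *b* ≥ 2. Counting the day of the rise as day 0 is my assumption; the SAP does not say.

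| Case | Protocol | 10-fold table | 30-day table |
|---|---|---|---|
| *a* = 4, *b* = 2.5, same draw | yes | no | yes |
| *a* = 12, *b* = 1 | yes | yes | no |
| *a* = 4, then *b* = 2.5 twenty days later | no | no | yes |
| *a* = 8, *b* = 1 | no | no | no |

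A same-draw case satisfies the 30-day rule with a gap of 0 days, and limb 2 is the 10-fold table itself. Every protocol case in the analysed data therefore appears in at least one of the two tables. A check on 200,000 randomly generated three-draw patients agreed: 0 protocol cases were missed and 1,321 were counted that did not meet the protocol rule. The 1,321 depends on arbitrary inputs and shows direction only.

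Neither table alone equals the protocol count, and the two cannot be added, because a patient can be in both.

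**Step 3. When can the 30-day table over-count?** In Year 1 the flow chart schedules safety laboratory tests on Days 1, 169 and 337. The planned gaps are 169 − 1 = 168 and 337 − 169 = 168 days. With a 14-day window at both ends, the later gap is at least 168 − 28 = 140 days, well over 30. The two rules can therefore differ only where extra draws are taken. A patient with a liver alert is a likely candidate, because follow-up under the DILI checklist may add blood samples.

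**Step 4. Size one unticked case** (Clopper-Pearson 95% intervals; planned N of about 40, at most 45, from protocol 7.5).

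- Upper limit for 0/*n*: 1 − 0.025^(1/*n*). For *n* = 40 this is 8.8%; for *n* = 45 it is 7.9%.
- For 1/40 = 2.5%: the lower limit is 1 − 0.975^(1/40) = 0.06%. The upper limit solves (1 − *p*)^40 + 40*p*(1 − *p*)^39 = 0.025, giving 13.2%.
- For 1/45 = 2.2%: 0.06% to 11.8%.

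**The case against.** The strongest reply is that a liver case would be seen anyway. SAP 7.8.2 tabulates the 10-fold limb at the protocol's own threshold, and Step 2 shows that the 30-day table takes in same-draw cases. All individual laboratory data are listed, with RCTC shift tables, a listing of potentially clinically significant values and the eDISH plot. Investigators must review central-laboratory reports, results also go to the sponsor, hepatic criteria trigger the DILI checklist, and AESIs are reportable within 24 hours. SAP 6.2 plans a general review of data discrepancies before lock. The infection and hypersensitivity classes already have search-based counts. All of this stands.

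It rules out several stronger readings that a reader might infer:

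- *That hepatic injury has no fallback.* The two laboratory tables together miss no case that has central-laboratory values in the analysed period.
- *That the SAP abandons the protocol criteria.* Its severe-infection heading keeps the RCTC reference, it assumes familiarity with the protocol, and the protocol definitions guide the investigator's classification.
- *That every AESI could be derived from the database.* Systemic hypersensitivity rests partly on clinical suspicion, so a derived count cannot replace the investigator there.
- *That the primary endpoint is affected.* It counts patients with any treatment-emergent AE, whether or not the AESI box is ticked.

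The reply does not remove the mismatch between the AESI table and the definition it carries. The discrepancy review is general and does not mention AESI ticks. The laboratory fallback also has limits. SAP 7.8.2 uses central-laboratory data unless otherwise specified, so a local-only result may be missed. It states no period for these frequency tables, while the SAP 6.1 on-treatment phase ends with the EoT visit.

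**Conclusion.** The concern holds in a limited form. The AESI table and summary line depend on the tick alone, so a case that meets the protocol definition can be absent from both. In the visible text, hepatic injury has no user-defined AE concept, no same-draw count and no single count of patients meeting either limb, and no reconciliation of ticks against definitions is planned.

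The consequence is an AESI count that may be incomplete or may disagree with other tables. It is not a lost liver signal, and no error rate is involved, since the trial is descriptive throughout. One unticked case moves the reported rate from 0/40 to 2.5%, with the upper 95% limit going from 8.8% to 13.2%. The frequency of unticked cases cannot be estimated from the documents.

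This rests on three assumptions: the 30-day window includes the day of the rise, about 40 patients are treated, and neither the SAP 5.4.1 list (cut off in the available copy) nor the sponsor's internal AE and laboratory standards already require such a reconciliation. The change is worth making because it is cheap and specific.

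**What to change.** In SAP 7.8.1:

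1. Keep the investigator-ticked AESI count.
2. Add a hepatic-injury flag derived from central-laboratory values by the protocol 5.2.6.1.4 rule: AST and/or ALT ≥ 3 times ULN with total bilirubin ≥ 2 times ULN "measured in the same blood draw sample", or AST and/or ALT ≥ 10 times ULN. Count each patient once and state the period covered.
3. Report the flag beside the ticked hepatic AESI count.
4. Compare ticked severe infections with the RCTC-grade concept already in Table 7.8.1:1.
5. List disagreements in both directions and query them before database lock.
6. Leave systemic hypersensitivity to the investigator's classification, supported by the existing SMQ searches.

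In SAP 7.8.2, keep the 30-day table as an additional display, label it as wider than the AESI definition, and say whether the day of the rise is included.

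The cost is a few lines of SAP text, one derived flag and one listing from data already collected. The AESI count may rise slightly. No clinical procedure changes.
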